4.2.2.2 Progression-free survival (PFS)

KM plots of PFS (based on the programmatically derived [RECIST 1.1] outcome) will be presented. Median PFS will be presented (calculated by the KM method).

Summaries of the number of percentage of patients experiencing a PFS event and the type of event (RECIST 1.1, or death) will also be provided. The analysis will be performed on the FAS.

The treatment status at the time of analysis will be summarized. This will include the number (%) of patients who were on treatment at the time of progression, the number (%) of patients

who discontinued study treatment prior to progression, the number (%) of patients who have not progressed and were on treatment or discontinued treatment.

4.2.2.3 Overall survival (OS)

KM plots as well as summaries of the number and percentage of patients who have died, those still in survival follow-up, those lost to follow-up, and those who have withdrawn consent will be provided along with the median OS (calculated using KM method) for each cohort.

4.2.2.4 Duration of response (DoR)

Descriptive data and KM plots of DoR will be presented. The median DoR will also be summarized, calculated by the KM method. Only patients who have a confirmed response will be included in this summary. This analysis will be performed on the evaluable for response analysis set.

Swimmer plots that clearly show the profile of each patient who responds will also be produced. This depicts each duration of response for each patient as a separate bar (horizontally) over time. Each cohort will appear on a separate plot.

Sensitivity analyses will be performed on FAS.

4.2.2.5 Best objective response (BoR)

Overall visit response data will be listed for all patients in the FAS, BoR will be summarized by n (%) for each category (CR, PR, SD, PD, and NE categories section 3.2.5).

4.2.2.6 Disease control rate (DCR)

For DCR, the point estimate and 90% CI (2-sided) will be presented at each timepoint (16 and 24 weeks). If the cohorts are expanded after the initial DRC, the CI will be calculated using an exact Mid-P method, otherwise an exact CI will be presented. This analysis will be performed on the evaluable for response analysis set.

Sensitivity analyses will be performed on FAS.

4.2.2.7 Proportion alive and progression-free at 12 and 18 months

APF12, and its 90% CI will be summarized (using KM methodology) and presented.

APF18 will be summarized as for APF12.

4.2.2.8 Overall survival at 12 and 24 months

OS12, and its 90% CI will be summarized (using KM methodology) and presented. OS24 will be summarized as per OS12.

4.2.2.9 Change in tumor size

The best change in TL tumor size from baseline, (where best change in TL size is the maximum reduction from baseline or the minimum increase from baseline in the absence of a reduction) will be summarized using descriptive statistics for each solid tumor cohort (SARCOMA and STO).

Tumor size will also be presented graphically using waterfall plots for each solid tumor cohort, to present each subject's best percentage change in tumor size as a separate bar, with the bars ordered from the largest increase to the largest decrease. Reference lines at the +20% and – 30% change in tumor size levels will be added to the plots, which correspond with the definitions of progression and 'partial' response respectively. All progressions will be marked with a '●' or designated with patterns or colors for ORR categories. The scale in these plots will be fixed to be from -100 to 100 to avoid presenting extreme values. Values that are capped as a result of this restriction to the scale are marked with '#'.

Additionally, 'spider' plots will be produced for each solid tumor cohort. This depicts each patient's percentage change in TL tumor size as a line over time and progression due to nontarget and/or new lesions will be indicated.

4.2.2.10 Overall RECIST response (Dose-finding)

No formal efficacy analysis will be performed for dose-finding cohorts, however a listing detailing overall RECIST response based on investigators assessment will be presented.

4.2.3 Safety analysis

Data from all cycles of treatment will be combined in the presentation of safety data. Safety summaries will be descriptive only. No formal statistical analyses will be performed on the safety variables.

4.2.3.1 DLT

The number and percentage of subjects with DLT during the dose finding phase will be presented by dose level based on DLT evaluable population.

4.2.3.2 Adverse events

AEs will be summarized separately for the periods defined in Section 3.3.1. AEs occurring pre-treatment or occurring post study treatment, or post-subsequent anti-cancer therapy will be listed, but not summarized separately.

An overall summary table will be produced showing the number and percentage of patients with at least 1 AE in any of the following categories: AEs, SAEs, deaths due to AE, AEs causing discontinuation of study treatment, and AESI/AEPI. The total number of AEs in the different AE categories in terms of AE counts will also be presented (i.e. accounting for multiple occurrences of the same event in a patient).

AEs will be summarized by system organ class (SOC) and PT assigned to the event using MedDRA. For each PT, the number and percentage of patients reporting at least one occurrence will be presented i.e. for 1 patient, multiple occurrences of an AE will only be counted once.

AEs (by SOC and PT) will be summarized by causality and maximum reported CTCAE grade. If a patient reports multiple occurrences of the same AE, maximum reported CTCAE grade will be taken as the highest recorded CTCAE grade for each SOC and PT.

Summary information (the number and percent of patients by SOC and PT, for each phase, will be tabulated for:

- All AEs
- Most common AEs
- All AEs by maximum reported CTCAE grade
- AEs of CTCAE grade 3 or 4
- Most common AEs of CTCAE grade 3 or 4
- Causally related AEs (to any study treatment)
- Causally related AEs of CTCAE grade 3 or 4
- AEs leading to dose interruption / discontinuation
- Dose limiting toxicities (based on DRC decision)

Death summaries and listings:

- All deaths
- AEs with an outcome of death
- AEs with an outcome of death – key patient information
- Listing of deaths

SAE summaries and listings:

- SAEs
- Causally related SAEs
- SAEs – listing of key information

AEs leading to discontinuation summaries and listings:

- AEs leading to discontinuation of any study treatment
- Causally related AEs leading to discontinuation of any study treatment
- AEs leading to discontinuation of study treatment – key patient information

AEs of special or possible interest summaries:

- AESI/AEPI list of PTs ^a
- AESI/AEPI by CTCAE grade
- AESI/AEPI by outcome
- AESI/AEPI with an outcome of no longer present, by time of resolution
- AESI/AEPI leading to dose interruptions or discontinuation

^a – AESI/AEPI PTs will be obtained from the AZ team (see section 3.3.1)

imAE:

The imAEs will be summarized in the same manner as for the summaries for AESI described above. The additional analyses include but not limited to, time to first onset imAE and resolution of imAE of Grade 3 or 4. See further details in the imAE Charter with respect to derivation rules.

In addition, the following analyses regarding systemic steroid use for imAE will be provided by imAE group. See further details in the imAE Charter with respect to derivation rules associated with duration and time to systemic steroid use for imAE. The duration of steroid use will be produced by imAE group for both all systemic steroids and high dose systemic steroids.

4.2.3.3 Clinical laboratory variables (clinical chemistry, hematology and urinalysis)

All laboratory safety data will be listed for each patient and summarized where appropriate. Clinical chemistry and hematology values outside the reference ranges will be highlighted in the listings. Data summaries will be provided in preferred units.

For continuous laboratory data absolute and change from baseline will be summarized by visit.

Box plots of change from baseline will be presented for haematology and clinical chemistry variables.

Shift tables for laboratory values by worst CTCAE grade will be produced, and for specific parameters separate shift tables indicating hyper- and hypo- directionality of change will be produced. The laboratory parameters for which CTCAE grade shift outputs will be produced are:

- Hematology: Hemoglobin (low and high), Leukocytes (low and high), Lymphocytes (low and high – absolute count), Neutrophils (low – absolute count), Platelets.
- Clinical chemistry: ALT (high), AST (high), ALP (high), Total bilirubin (high), Albumin (low), Magnesium (hypo and hyper), Sodium (hypo and hyper), Potassium (hypo and hyper), Corrected calcium (hypo and hyper), Glucose (low), Creatinine (high).

For urinalysis a shift table comparing baseline to the maximum on-treatment value will be presented.

Hy's law

The following summaries will include the number (%) of patients who have:

- Elevated ALT, AST, and Total bilirubin during the study
 - ALT $\geq 3\times$ - $\leq 5\times$, $> 5\times$ - $\leq 8\times$, $> 8\times$ - $\leq 10\times$, $> 10\times$ - $\leq 20\times$, and $> 20\times$ Upper Limit of Normal (ULN) during the study
 - AST $\geq 3\times$ - $\leq 5\times$, $> 5\times$ - $\leq 8\times$, $> 8\times$ - $\leq 10\times$, $> 10\times$ - $\leq 20\times$, and $> 20\times$ ULN during the study
 - Total bilirubin $\geq 2\times$ - $\leq 3\times$, $> 3\times$ - $\leq 5\times$, $> 5\times$ ULN during the study
 - ALT or AST $\geq 3\times$ - $\leq 5\times$, $> 5\times$ - $\leq 8\times$, $> 8\times$ - $\leq 10\times$, $> 10\times$ - $\leq 20\times$ and $> 20\times$ ULN during the study
 - ALT or AST $\geq 3\times$ ULN and Total bilirubin $\geq 2\times$ ULN during the study (potential Hy's law). Note: Note: The onset date of ALT or AST elevation should be prior to or on the date of total bilirubin elevation.
- Narratives will be provided in the CSR for patients who have ALT $\geq 3\times$ ULN plus Total bilirubin $\geq 2\times$ ULN or AST $\geq 3\times$ ULN plus Total bilirubin $\geq 2\times$ ULN at any visit.

Liver biochemistry test results over time for patients with elevated ALT (i.e. $\geq 3 \times$ ULN) or AST (i.e. $\geq 3 \times$ ULN), and elevated Total bilirubin (i.e. $\geq 2 \times$ ULN) (at any time) will be plotted. Individual patient data where ALT or AST (i.e. $\geq 3 \times$ ULN) plus Total bilirubin (i.e. $\geq 2 \times$ ULN) are elevated at any time will be listed also.

Plots of ALT and AST versus total bilirubin by cohort will also be produced with reference lines at $3 \times$ ULN for ALT, AST, and $2 \times$ ULN for total bilirubin. In each plot, total bilirubin will be in the vertical axis.

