2.3.2.2 Tremelimumab

Risks with tremelimumab monotherapy include in adults, but are not limited to, GI effects (colitis, diarrhea, enterocolitis, and intestinal perforation); endocrine disorders (hypo- and hyperthyroidism, hypophysitis, and adrenal insufficiency); skin effects (rash and pruritus); elevations in lipase and amylase and clinical manifestations of pancreatitis, other GI events (eg, ulcerative colitis, dehydration, nausea, and vomiting); hepatic events (including hepatitis and liver enzyme elevations); pneumonitis and ILD; nervous system events (including encephalitis, peripheral motor and sensory neuropathies, Guillain-Barré, and proximal muscle weakness); cytopenias (including thrombocytopenia, anemia, and neutropenia); infusion-related reactions, anaphylaxis, and allergic reactions; renal events (including renal failure, acute kidney injury, nephritis, nephrotic syndrome, and autoimmune nephritis); and electrolyte abnormalities (eg, hypokalemia); autoimmune diseases (including autoimmune arthritis, Sjogren's syndrome, and giant cell temporal arteritis); hyperglycemia and diabetes mellitus; and pyrexia.

For information on all identified and potential risks with tremelimumab, please always refer to the current version of the tremelimumab IB.

In monotherapy clinical studies in adults, AEs typically reported very commonly include events such as diarrhea, nausea, fatigue, pruritus, decreased appetite, rash, vomiting, dyspnea, constipation, cough, pyrexia, abdominal pain, decreased weight, headache, asthenia, and anemia. Approximately 16% of patients experienced an AE that resulted in permanent discontinuation of tremelimumab, and approximately 45% of patients experienced an SAE. Please see the current version of the IB for a detailed summary of monotherapy data, including AEs, SAEs, and NCI CTCAE Grade 3 to 5 events reported across the tremelimumab program.

A detailed summary of tremelimumab monotherapy AE data can be found in the current version of the tremelimumab IB.

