8.3.13 Adverse events of special interest

An AESI is one of scientific and medical interest specific to understanding of the IP and may require close monitoring. An AESI may be serious or non-serious. The rapid reporting of AESIs allows ongoing surveillance of these events in order to characterize and understand them in association with the use of this IP.

Adverse events of special interest for durvalumab ± tremelimumab include but are not limited to events with a potential inflammatory or immune-mediated mechanism and which may require more frequent monitoring and/or interventions such as steroids, immunosuppressants and/or hormone replacement therapy. These AESIs are being closely monitored in clinical studies with durvalumab monotherapy and combination therapy. An imAE is defined as an AESI that is associated with drug exposure and is consistent with an immune-mediated mechanism of action and where there is no clear alternate etiology. Serologic, immunologic, and histologic (biopsy) data, as appropriate, should be used to support an imAE diagnosis. Appropriate efforts should be made to rule out neoplastic, infectious, metabolic, toxin, or other etiologic causes of the imAE.

If the Investigator has any questions in regards to an event being an imAE, the Investigator should promptly contact the Study Physician.

AESIs observed with durvalumab ± tremelimumab include:

- Diarrhea/colitis and intestinal perforation
- Pneumonitis/ILD
- Endocrinopathies (ie, events of hypophysitis/hypopituitarism, adrenal insufficiency, hyper- and hypo-thyroidism and type I diabetes mellitus)
- Hepatitis/transaminase increases
- Nephritis/blood creatinine increases
- Pancreatitis/serum lipase and amylase increases

- Rash/dermatitis
- Myocarditis
- Myositis/polymyositis
- Neuropathy/neuromuscular toxicity (eg, Guillain-Barré, and myasthenia gravis)
- Other inflammatory responses that are rare/less frequent with a potential immune-mediated etiology include, but are not limited to, pericarditis, sarcoidosis, uveitis, and other events involving the eye, skin, hematological, neuromuscular toxicities (eg, Guillain-Barré syndrome, myasthenia gravis) and rheumatological events.

In addition, infusion-related reactions and hypersensitivity/anaphylactic reactions with a different underlying pharmacological etiology are also considered AESIs.

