AESI/AEPIs include but are not limited to events with a potential inflammatory or immune-mediated mechanism and which may require more frequent monitoring and/or interventions such as steroids, immunosuppressants and/or hormone replacement therapy. These AESI/AEPIs are being closely monitored in clinical studies with durvalumab monotherapy and combination therapy.

AESI/AEPIs observed with durvalumab ± tremelimumab include but are not limited to:

- Diarrhea/colitis and intestinal perforation
- Pneumonitis/ interstitial lung disease
- Endocrinopathies (i.e. events of hypophysitis/hypopituitarism, adrenal insufficiency, hyper and hypothyroidism and type I diabetes mellitus)
- Hepatitis/transaminase increases
- Nephritis/blood creatinine increases
- Pancreatitis/serum lipase and amylase increases
- Rash/dermatitis
- Myocarditis
- Myositis/polymyositis
- Other inflammatory responses that are rare/less frequent with a potential immune-mediated etiology include, but are not limited to, pericarditis, sarcoidosis, uveitis, and other events involving the eye, skin, hematological, and rheumatological events.

In addition, infusion-related reactions and hypersensitivity/anaphylactic reactions with a different underlying pharmacological etiology are also considered AESIs.

Other categories may be added as necessary or existing terms may be merged. An AstraZeneca medically qualified expert after consultation with the Global Patient Safety Physician has reviewed the AEs of interest and identified which HLTs and which PTs contribute to each AESI/AEPI. Further reviews may take place prior to database lock to ensure any further terms not already included are captured within the categories.

Immune-Mediated Adverse Events (imAE)

Sponsor will perform medical review of those AESIs and classify them as immune-mediated AEs (imAEs) or not imAEs. Further details are provided in an imAE Charter.

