3.3.2 Laboratory data

Blood and urine samples for determination of clinical chemistry, hematology, and urinalysis will be taken at the times indicated in the assessment schedules and as clinically indicated Sections 1.1 and 8.2.1 of the CSP.

Change from baseline in hematology and clinical chemistry variables will be calculated for each post-dose visit on treatment. CTCAE grades will be defined at each visit according to the CTCAE grade criteria using local ranges as required, after conversion of lab result to corresponding preferred unit. The following parameters have NCI CTCAE grades defined for both high and low values: Hemoglobin, Leukocytes, Lymphocytes, Potassium, Sodium, Magnesium and Corrected calcium so high and low CTC grades will be calculated.

Absolute values will be compared to the local laboratory reference ranges and classified as low (below range), normal (within range or on limits of range) and high (above range).

The maximum or minimum on-treatment value (depending on the direction of an adverse effect) will be defined for each laboratory parameter as the maximum (or minimum) post-baseline value at any time.

Corrected calcium product will be derived during creation of the reporting database using the following formula:

$$\text{Corrected calcium (mmol/L)} = \text{Total calcium (mmol/L)} + ([40 - \text{albumin (G/L)}] \times 0.02)$$

Project reference ranges will be used for the primary interpretation of laboratory data. Local reference ranges will be used for analysing laboratory data at the local laboratory. The denominator used in laboratory summaries of CTCAE grades will only include evaluable patients, in other words those who had sufficient data to have the possibility of an abnormality.

For example:

- If a NCI CTCAE criterion involves a change from baseline, evaluable patients would have both a pre-dose and at least 1 post dose value recorded.
- If a NCI CTCAE criterion does not consider changes from baseline to be evaluable, the patient need only have 1 post dose value recorded.

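### No planned table counts patients whose serum glucose moves to high, although hyperglycemia and type I diabetes are the named risks

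*SAP*

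**What the plan says.** SAP 4.2.3.3 states: "Shift tables for laboratory values by worst CTCAE grade will be produced". The list that follows gives magnesium, sodium, potassium and corrected calcium in both directions, and glucose in one: "Corrected calcium (hypo and hyper), Glucose (low), Creatinine (high".

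SAP 3.3.2 names the parameters that have CTCAE grades in both directions: "Hemoglobin, Leukocytes, Lymphocytes, Potassium, Sodium, Magnesium and Corrected calcium so high and low CTC grades will be calculated". Glucose is not among them. The same section classifies every absolute value as low, normal or high against the local laboratory range. It also defines an extreme value per parameter: "The maximum or minimum on-treatment value (depending on the direction of an adverse effect".

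On risk, protocol 2.3.2.2 includes "hyperglycemia and diabetes mellitus" for tremelimumab, and protocol 2.3.2.1 includes type I diabetes mellitus for durvalumab. The list of adverse events of special interest in protocol 8.3.13 has "hyper- and hypo-thyroidism and type I diabetes mellitus", and SAP 3.3.1 has "hyper and hypothyroidism and type I diabetes mellitus". Hypoglycemia appears in none of these lists.

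**The concern.** The one table that would give a patient count for serum glucose points away from the known harm. A reader of the study report could see how many children shifted to a worse low-glucose grade, but not how many went from a normal baseline to a high value.

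This matters because the adverse event tables do not reliably fill the gap. Glucose is in the protocol-mandated chemistry panel (protocol Table 19). Under protocol 8.3.7, deterioration in a mandated laboratory value becomes an adverse event only if it meets a seriousness criterion or is the reason for stopping treatment. Associated signs and symptoms are reported in their own right. A rise that is asymptomatic, non-serious and does not end treatment therefore depends on the laboratory outputs alone. Safety is a primary objective in dose-finding and a stated objective in dose-expansion.

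**Working it through.** The plan gives no figure to reproduce. The check sets each planned output beside the question it would have to answer: how many patients moved from normal to high serum glucose?

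1. **CTCAE shift table (SAP 4.2.3.3).** Low direction only. It does not answer the question.
2. **By-visit summaries (SAP 4.2.3.3, with SAP 4.1).** Continuous data are summarized with minimum and maximum, so a high value can be seen. There are two limits in SAP 4.1.3. Only the value closest to the scheduled date in each window is used, so an unscheduled peak can drop out. In dose-expansion, a visit is summarized only if it passes a threshold built on 5 observations, so later visits in small cohorts may not appear. A visit maximum also does not say how many patients were high, or from what baseline.
3. **Box plots of change from baseline.** These show spread, not a count.
4. **Listings.** Chemistry values outside the reference range are highlighted per patient. The information is there, but the reader has to do the counting.
5. **Urinalysis shift table (SAP 4.2.3.3).** Urine glucose is in the panel (protocol Table 21), and the table runs from baseline to maximum on-treatment value. This is a patient-level table in the right direction, but for urine. Protocol Table 3 schedules chemistry and not urinalysis after treatment ends, while SAP 3.3 counts laboratory assessments up to 90 days after the last dose as on-treatment.
6. **Adverse event, AESI and imAE tables (SAP 4.2.3.2).** Diagnosed type I diabetes and any reported hyperglycemia are counted. Rises not reportable under protocol 8.3.7 are not.

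None of the six gives the count.

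**Size of one patient in the missing table.** The documents plan 26 evaluable SARCOMA patients (11 if the cohort stops at stage 1) and 10 evaluable STO patients:

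- 1/26 = 3.8%
- 1/11 = 9.1%
- 1/10 = 10.0%

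Safety tables include all dosed patients, so the real denominators may be somewhat larger and the percentages smaller.

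**Illustration of item 2, with assumed glucose values.** One child in 26 rises from 5 to 15 mmol/L and the others do not change. The mean change is (15 − 5)/26 = 0.38 mmol/L. If that value is the one selected for the window, the same table prints a maximum change of 10 and a maximum value of at least 15 mmol/L. The low-direction shift table gains 0 patients. A high-direction table would show 1/26.

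**The case against.** The best defense is that the list in SAP 4.2.3.3 governs CTCAE-grade shifts only, and SAP 3.3.2 presents its two-direction list as the parameters for which such grades exist. Glucose is absent from that list, so a one-direction grade table follows. This stands. The two sections agree with each other, and the entry looks deliberate. The CTCAE criteria are not reproduced in the documents, so whether a laboratory grade for high glucose could be derived cannot be settled here. What the defense does not explain is why no other table counts patients in the high direction, since the reference-range class needs no CTCAE grade.

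A reader might infer that 4.2.3.3 contradicts the maximum-or-minimum rule in SAP 3.3.2. The documents do not support that. The rule is a separate derivation for each parameter, and 4.2.3.3 lists grade shifts without redefining it.

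A reader might also infer that a glucose rise would be invisible or lost in averages. That is not supported either: by-visit tables print the maximum, out-of-range values are flagged in listings, urine glucose has its own shift table, and diabetes is counted among the events of special interest.

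Finally, a count of high values would be hard to interpret. The glucose entry in protocol Table 19 carries no fasting condition, and protocol Table 16 allows immunosuppressive medication, which includes systemic corticosteroids, for managing treatment-related events. Meals and steroids can both raise glucose. This stands as a limit on interpretation. It is not a reason to leave the count out of a descriptive table.

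**Conclusion.** The point holds in a limited form. Serum glucose has a shift table in the low direction only, the named risks lie in the high direction, and no planned table counts patients who moved to high. The rises most likely to go uncounted are asymptomatic, non-serious ones that do not stop treatment. Even these remain in the listings, and may appear in by-visit maxima and the urine-glucose table.

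The consequence is modest. SAP 4.2.3 describes the safety summaries as descriptive only, and nothing here affects the primary endpoint, the error rates or a stopping rule. The change is still worth making because it gives a direct count for a named risk from quantities already derived. The conclusion assumes that no table of high serum glucose is specified in a document not available here, such as the output shells or the imAE charter.

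**What to change.** In SAP 4.2.3.3, add one serum glucose shift table for each phase: baseline class against class at the maximum on-treatment value, using the low/normal/high reference-range classes from SAP 3.3.2. State that the maximum is taken over all on-treatment values, including unscheduled ones, in line with the rule for extreme values in SAP 4.1.3. Keep the low-direction CTCAE table. Add a footnote saying that samples were not required to be fasting and that steroids were permitted for managing adverse events, so the high count is descriptive and does not by itself attribute the rise to study drug.

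The cost is one additional table shell and its programming. No new data, visits or samples are needed, and no clinical rule changes.
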